1.0 Introduction

Lead durability and integrity depend on several factors, such as lead design, lead material, and mechanical stress. More than half of all lead complications are insulation defects, most frequently due to subclavian crush syndrome, abrasion of the lead by direct contact to the pulse generator (i.e. pacemaker, ICD, or CRT-D), or abrasion of the lead against adjacent leads. Often these present clinically with evidence of impedance changes or inappropriate ventricular sensing and defibrillation¹.

St. Jude Medical Riata® and Riata® ST family of leads are high voltage implantable cardioverter defibrillator (ICD) endocardial leads with Silicone insulation. QuickSite® and QuickFlex® left ventricular leads also utilize silicone rubber for insulation. Silicone rubber, while representing the industry's most commonly used defibrillation lead insulation material over the past 20 years, has been observed to be vulnerable to abrasion^{2,3,4}. Abrasion of silicone defibrillation leads is acknowledged within the clinical community as a well known clinical risk and is well documented in the literature as the number one cause of lead failure across the industry with reported failure rates ranging from 3 to 10 %^{5,6,7}.

A more recently reported manifestation of Riata lead insulation and QuickSite/QuickFlex lead abrasion involves conductors that are outside the lead body as detected by x-ray, fluoroscopy, or post-explant physical examination. This phenomenon, known as inside-out abrasion with externalized conductors, occurs when internal abrasion processes produce an outer insulation breach significant enough to allow the conductor to separate from the lead body in isolated regions. Such a separation does not guarantee an electrical abnormality because the conductors themselves are insulated with a robust layer of ethylenetetrafluoroethylene (ETFE) polymer.

The prevalence of externalized conductors proximal to the RV coil in Riata/Riata ST leads has been reported to vary from 0.5% to 33.3% depending on the lead model⁸⁻¹¹. Some of these cases of externalized conductors have been accompanied with inappropriate shocks, oversensing, increased pacing impedance/ threshold and lead noise. It remains unclear whether externalized conductors caused these electrical problems, as approximately 85% of the returned leads with externalized conductors do not have their ETFE insulation compromised and therefore should not be the cause of any reported electrical problem.

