3.0 Clinical Protocol

3.1 Study Design and Scope

This study is a prospective, non-randomized, multi-center, international post market study that will determine the prevalence and incidence of externalized conductors and other visual lead anomalies (as evidenced by imaging) and the risk of progression to electrical dysfunction in a large series of ICD/ CRT-D/CRT-P devices containing one or more of the following SJM leads: Riata leads, Riata ST silicone leads, Durata leads, QuickSite/QuickFlex CRT leads. A patient that has at least one market released lead implanted in time period indicated in Table 1 is eligible for enrollment in the study. Each lead group will be considered separately for independent analysis.

Table 1: Leads Eligible for Enrollment

Lead Group	Model Numbers	Lead Implant Date
Riata	1560, 1561, 1562, 1570, 1571, 1572, 1580, 1581, 1582, 1590, 1591, 1592	2002-2009
Riata ST Silicone	7000, 7001, 7002, 7010, 7011, 7040, 7041, 7042	2006-2009
QuickSite/QuickFlex	1056T, 1058T, 1156T, 1158T	2006-2010
Durata	7120, 7121, 7122, 7130, 7131, 7120Q, 7121Q, 7122Q, 7170Q, 7171Q, 7172Q	2008-2010

In order to determine the prevalence and incidence of externalized conductors, other visual lead anomalies as well as electrical dysfunction in the population of leads being evaluated, a minimum of 1500 leads listed above will be enrolled at up to 60 sites. This will comprise a minimum of 300 leads in the Riata lead group and a minimum of 200 leads in the Riata ST lead group to make a combined total of at least 500 Riata and Riata ST silicone leads. The study will also include at least 500 leads in the QuickSite/QuickFlex and Durata lead groups. All patients will be followed every six months for three years.

Adequate representation across the different ages of the leads is also needed to understand the lead population being studied. Therefore, the leads from each group of leads will be compromised of subgroups based on the age of lead (at enrollment) being studied. The required minimum enrollment for each subgroup per lead group is indicated in Table 2. Even if the minimum enrollments indicated in Table 2 are met, extra enrollments may be required to ensure a minimum of 500 leads in each lead group.

Expected Attrition in patients with high voltage leads

Withdrawals due to death

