Demographic and clinical parameters will be compared between patients who experience electrical dysfunction and those who do not experience electrical dysfunction. Specifically, the variables age, gender body mass index, lead size, lead model, and implant factors such as venous access site, number of other leads in the vasculature, fixation location in the right ventricle, level of activity (based on functional NYHA class scale I, II, III, IV), level of therapy that patient received (no ATP/shock, ATP or shock) and slack in the lead (grades 0, 1, 2, 3, 4 based on the scale described by Ha et al, 2010¹²) will be used for the comparison. Continuous variables such as age or body mass index will be compared using Student's T-tests while categorical variables such as gender or lead models will be compared using Pearson's Chi-square statistic. Point estimates and p-values will be provided from these analyses.

In addition, the two patient groups will be compared for the following endpoints:

1. Frequency of externalized conductors. This will be done using a Pearson's Chi-square analysis.
2. Frequency of other visual lead anomalies. This will be done using a Pearson's Chi-square analysis.
3. Time to detection of externalized conductors. A Kaplan-Meier analysis will be used for this comparison.
4. Time to detection of other visual lead anomalies. A Kaplan-Meier analysis will be used for this comparison.
5. The extent of externalization will be compared using Pearson's Chi-square analysis.
6. Number of zones with externalization within one lead will be compared using a Student's T-test.
7. Location of externalization will be compared using Pearson's Chi-square analysis.
8. Amount of slack in the lead (based on the scale described by Ha et al, 2010)¹² will be compared using Pearson's Chi-square analysis.

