11.2 Cinefluoroscopy Adjudication Committee

Cinefluoroscopy Adjudication Committee (CAC) will be comprised of at least three Electrophysiologists or Cardiologists specially trained in using Cinefluoroscopy in this patient population. The role of the CAC is to adjudicate the cinefluoroscopy videos/images to determine the presence of lead compromise in the SJM Cardiac Lead Assessment study patient population. Committee members will be reviewing the cinefluoroscopy videos/images for the enrollment, 12, 24, and 36 month follow-up visits and any additional cinefluoroscopy videos/images received during the course of the study. Data will be sent either electronically or on a disk to the committee members. Once the adjudication is complete, a cinefluoroscopy adjudication form will be collected per patient per study visit. If the presence of externalized conductors is deemed to be ‘indeterminate’ then the cinefluoroscopy will be further reviewed by two other CAC members. Sample pictures/fluoros/x-rays and other examples of “other visual lead anomalies” will be provided to the adjudication committee to aid the committee members in identifying these “other visual lead anomalies” on the cinefluoroscopy videos/images received from the site.

Only the adjudicated imaging data will be included in the post market surveillance reports. Percentage of leads with compromise, evidenced by imaging, will be presented in the report. The type, extent and location of

lead compromise, as described in Appendix A, will also be included. As detailed in Appendix A, each region of the HV as well as CRT leads is divided into different regions. Both the proximal as well as distal ends of externalization will be recorded by the cinefluoroscopy adjudication committee. The distribution of externalization (both absolute number and percentage) by each region of the lead will be presented for both proximal and distal ends of externalization. The distribution of “other visual lead anomalies” (both absolute number and percentage) by each region of the lead and each individual subcategory of “other visual lead anomalies” will be presented. The frequency (both absolute number as well as percentage) of individual subcategories will be reported for “other visual lead anomalies”.

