Appendix A: Details About Lead Compromise

[figure not shown]
Lead Compromise as evidenced by imaging includes externalized conductors or other visual lead anomalies. The types, extent and location of these anomalies in high voltage (HV) leads are listed below:

Type	Extent	Location on the lead (see figure below)
Externalized Conductors	- Apparent width and length of externalized conductors on fluoroscopy	- Region 1 - Region 2 - Region 3 - Region 4
Other Visual Lead Anomalies	- Fracture - Subclavian crush - Kink - Broken filars on a shocking coil - Other irregularities	- Region 1 - Region 2 - Region 3 - Region 4 - RV coil - SVC coil - Distal to RV coil - Proximal to region 1

Similarly, the type, extent and location of these anomalies in CRT leads are listed below:

Type	Extent	Location on the lead (see figure below)
Externalized Conductors	- Apparent width and length of externalized conductors on fluoroscopy	- Region a - Region b - Region c - Region d
Other Visual Lead Anomalies	- Fracture - Kink - Subclavian crush - Other irregularities	- Region a - Region b - Region c - Region d

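### Extent of externalization is recorded as width and length but is to be compared by Pearson's chi-square, with no classes stated

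*Combined protocol and SAP*

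**What the plan says.** Appendix A has a column for the extent of each type of lead compromise. For externalized conductors the entry is "Apparent width and length of externalized conductors on fluoroscopy", in the table for high-voltage leads and again in the table for CRT leads. No grades, bins or thresholds are given, and nothing says how width and length combine. Section 11.2 adds none: the type, extent and location of "lead compromise, as described in Appendix A, will also be included" in the reports.

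Section 3.2.2.10 compares patients who have electrical dysfunction with those who do not. Its list of additional endpoints has as item 5: "The extent of externalization will be compared using Pearson's Chi-square analysis".

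Three other entries in the same section show how it treats other variables:
- For demographic and clinical variables: "Continuous variables such as age or body mass index will be compared using Student's T-tests", with chi-square kept for categorical ones.
- Endpoint 6, the number of externalized zones within a lead, goes to a t-test.
- Endpoint 8, lead slack, goes to chi-square, but its classes are stated: "slack in the lead (grades 0, 1, 2, 3, 4 based on the scale described by" a cited publication.

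**The concern.** A width and a length are measured quantities. Chi-square cannot use them until they are cut into classes, and the plan names no classes. Extent is therefore handled unlike the measured variables in the same section, which go to a t-test, and unlike slack, which has stated grades. Endpoint 5 cannot be carried out from the text alone.

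Two things are at stake. Grouping discards information, so a real relation between the size of an externalization and electrical failure is easier to miss. An unstated cut can also be settled after the results are known, and then the p-value no longer means what it says. Section 1.0 states that the study should inform physicians about whether externalized conductors with normal function may progress to malfunction. Endpoint 5 is the only planned comparison of measured length and width with dysfunction.

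**Working it through.** **No planned figure to reproduce.** The documents give no power, effect size, SD, significance level or expected group sizes for this endpoint. The section's main comparisons promise only that "Point estimates and p-values will be provided from these analyses". Everything below is illustrative: two-sided 5%, equal SDs, and a shift on the measured (or log) scale.

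**Plausible numbers.** Section 1.0 says prevalence in Riata/Riata ST leads "has been reported to vary from 0.5% to 33.3% depending on the lead model". Section 3.1 sets minimum enrolment "to make a combined total of at least 500 Riata and Riata ST silicone leads". So 0.005 × 500 = 2.5 and 0.333 × 500 = 166.5, or about 3 to 167 externalized leads. The share with dysfunction is not given. Applying the 3-10% failure range that section 1.0 quotes for silicone leads gives 0.03 × 167 ≈ 5 to 0.10 × 167 ≈ 17. Higher shares were also tried.

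**Large-sample loss from a median split.** Under normality its efficiency relative to the t-test is 2/π, so

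power after split = Φ(√(2/π) × (z₀.₉₇₅ + z_power) − z₀.₉₇₅).

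At 80% t-test power: 0.798 × (1.960 + 0.842) − 1.960 = 0.275, and Φ(0.275) = 0.608. The loss is 80 − 60.8 = 19.2 points. The finite-sample formula (20 patients in the smaller group, ratios 1:1 to 1:9) gives 21-23 points at 80% power, 17-18 at 50%, and about 6 at 20%.

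**Simulation with the t-test set at about 80% power** (3,000 replicates per row, power in %):

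| Externalized leads | Share with dysfunction | Rank-sum | Chi-square, median split | Loss against rank-sum |
|---|---|---|---|---|
| 50 | 10% | 73 | 56 | 17 |
| 50 | 20% | 75 | 66 | 9 |
| 100 | 10% | 76 | 69 | 7 |
| 100 | 30% | 76 | 59 | 17 |
| 165 | 20% | 78 | 60 | 18 |
| 165 | 30% | 77 | 61 | 16 |

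Against the rank-sum test the loss is 7-18 points. Against the t-test the formulas above give 19-23. The same rows set against a nominal 80% give 11-24; the top value agrees with 23 within simulation error (about 1 point).

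**The low end is flattering to chi-square.** With 10 dysfunctions among 100 leads, 50 leads lie above the median. The uncorrected test rejects when 8 or more, or 2 or fewer, of the 10 lie above it (at 8, z = (8/10 − 42/90)/√(0.25 × (1/10 + 1/90)) = 2.0). Under no difference that has probability 2 × [C(50,8)C(50,2) + C(50,9)C(50,1) + C(50,10)]/C(100,10) = 9.2%, not 5%. The 7 points are therefore not a comparison of tests with equal size.

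**How far the loss can move, at 167 leads** (10,000 replicates unless marked; d is the standardized shift, on the log scale for lognormal data):
- 5 vs 162, d = 1.0, by formula: t-test 59.6%, split 28.0%, loss 31.6 points.
- 15 vs 152, d = 0.8: 84.1% vs 51.9%, loss 32.2 points. Here the split is conservative (3.0% under no difference).
- 17 vs 150, d = 0.8: 87.7% vs 63.4%, loss 24.3 points.
- 10 vs 157, d = 0.5: 32.9% vs 32.2%, loss 0.7 points. Rank-sum is 1.6 points behind the split.
- Lognormal, 25 vs 142, d = 0.5: t-test ahead by 1.5 points, rank-sum by 8.9.

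In a separate lognormal run with 50 vs 50 and d = 0.3 to 0.8, the t-test is 4-6 points behind the split, while rank-sum is 4-10 points ahead.

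**A free choice of cut.** With no true difference, 50-165 externalized leads and 10-30% dysfunction, taking the smallest p-value from cuts at the lower third, median and upper third gives about 9-13% false positives.

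**The case against.** The strongest reply is that the text may simply be incomplete. The cinefluoroscopy adjudication form mentioned in section 11.2 is not in the documents, and apparent width and length may be graded on it. The extent column of Appendix A does hold categories for other anomalies, such as fracture or kink. If grades exist, chi-square is workable. This stands as a reason not to claim too much, but the plan would still need to state the grades, as it does for slack. Chi-square would also ignore their order.

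A reader might infer three stronger things:
- *That the cut will be chosen after the data are seen.* The documents show only that no cut is stated. A choice after the fact is possible, not established.
- *That nothing else relates the size of externalization to dysfunction.* Endpoint 6 compares the number of externalized zones by a t-test, and that is a related size measure.
- *That a definite amount of power is lost.* The plan never mentions a median split and gives no group sizes or effect. Any single figure comes from the assumptions made.

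It is also fair to say that the section's own convention would point to a t-test, and that naming classes in advance would close the gap in specification. Both are improvements. With skewed lengths the t-test can do worse than the split, and classes still discard the scale, so a rank test is the safer choice.

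Finally, this is one of eight additional comparisons within a secondary outcome of a largely descriptive study. That limits its importance.

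**Conclusion.** The point holds as a mismatch between how extent is recorded and how it is to be tested. A measured width and length are sent to a test for classes that the plan does not define, contrary to how the section treats its other measured variables.

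The cost is illustrative. It is roughly 7-23 points of power for a median split, assuming a normal shift, a two-sided 5% level and about 80% t-test power; the lower part of that range takes the rank-sum test as comparator and the upper part the t-test. Sparse or skewed data widen it to between near zero and just over 30 points, partly because the split test's true size drifts from 5%. A cut picked from three would give about 9-13% false positives, which is a risk that the text leaves open and not a prediction. The primary prevalence and hazard-rate outcomes are unaffected. The change should be made, but the study does not turn on it.

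**What to change.** Replace endpoint 5 of section 3.2.2.10 with:

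> Apparent length and apparent width of externalization, as adjudicated (largest value per patient if several zones or leads are externalized), will each be compared between externalized patients with and without electrical dysfunction on the measured scale by the Wilcoxon rank-sum test, with medians and the Hodges-Lehmann difference with 95% CI. Any grouped presentation is descriptive.

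The rule on the largest value is needed because section 3.2.2.10 compares patients, while endpoint 6 expects several zones in one lead and a patient may carry more than one study lead. The restriction to externalized patients is needed because width and length exist only for them.

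If the adjudication form turns out to record only ordered grades, state those grades in Appendix A and apply the same rank test to them. Keep chi-square for location (endpoint 7), which is categorical.

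The cost is one sentence of analysis text. No new data are needed provided the form holds numerical width and length, as Appendix A implies; this should be checked against the form.

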3.2.3 Additional Data

- Adverse events
- Lead Electrical Measurements: capture threshold, signal amplitude and impedance
- Types of clinical interventions following externalized conductors
- Types of clinical interventions following other visual lead anomalies
- Types of events leading to detection of externalized conductors
- Types of events leading to detection of other visual lead anomalies by each subcategory
- Types of events leading to detection of electrical dysfunction

3.3 Patient Selection

3.3.1 Inclusion Criteria

Eligible patients will meet **all** of the following:

1. Patient has a market released SJM ICD, CRT-D or CRT-P already implanted.
2. Patient has at least one market released Riata/ Riata ST/QuickSite/QuickFlex/Durata already implanted in which the lead model number and lead implant date is indicated in Table 1.*
3. Have the ability to provide informed consent for study participation and be willing to comply with the prescribed evaluations as detailed in this study plan.
4. Are 18 years or above.

*As different subgroups reach the minimum number of patients required for analysis, St. Jude Medical may notify the sites in writing that enrollment for a specific age of lead within a lead group are no longer eligible for enrollment. This will ensure a more even distribution of lead ages and lead types across the study population.

3.3.2 Exclusion Criteria

Patients will be excluded if they meet **any** of the following:

1. Patient is currently pregnant.
2. *Enrolled or intend to participate in a clinical drug and/or device study, which could confound the results of this trial as determined by SJM, during the course of this clinical study.

*NOTE: Patients enrolled in St. Jude Medical SJ4 post approval study, OPTIMUM and SCORE registries can be enrolled in this study.

3.4 Study Procedures

Study procedures are described in the sections below. Refer to Table 3 for an overview of the required study procedures. St. Jude Medical will provide supplemental step by step instructions for obtaining required study data.

Table 3: Study Procedures

	Enrollment	6, 18, and 30 month visit	12, 24, and 36 month visit	Unscheduled visit	Extended 42 month visit ^c	Extended 48 month visit ^c
Informed Consent	✓					
Demographics	✓					
Medical History	✓					
Electrical Malfunction History	✓					
Cinefluoroscopy (AP, LAO 45° or the best possible LAO view, RAO 45° or the best possible RAO view)	✓ ^a		✓			✓ ^c
Chest X-ray or Any Imaging Study	✓ ^b					
Lead Measurements	✓	✓	✓	✓	✓ ^c	✓ ^c

a - Patients who underwent cinefluoroscopy at enrollment as part of the “Riata Lead Evaluation Study” will not be required to undergo another baseline cinefluoroscopy.

b - In patients with evidence of externalized conductors under cinefluoroscopy at enrollment, the following chest x-ray or imaging study will be collected, if available: a) earliest chest x-ray or imaging study with evidence of externalized conductors and b) latest chest x-ray or imaging study with no evidence of externalized conductors.

c - *For only eligible patients with QuickSite/QuickFlex leads that consent for an additional year of follow-up (42 and 48 Month Visits).*

3.4.1 Enrollment

Upon determination of study eligibility, informed consent will be obtained from eligible patients by the principal investigator or designee prior to initiation of any study related screening activities.

Patients with Riata, Riata ST, QuickSite (1056T or 1058T), QuickFlex (1156T or 1158T), and Durata leads with model numbers and lead implant dates indicated in Table 1 will be screened for evidence of externalized conductors or other visual lead anomalies through cinefluoroscopy that will include three videos/cines of the entire lead length as well as the pocket area (AP, LAO 45° or best possible LAO, RAO 45° or best possible RAO). A copy of Cinefluoroscopy performed as part of separate screening can be used to determine the incidence of externalization as long as all three views (AP, LAO 45° or the best possible LAO view, RAO 45° or the best possible RAO view) are available. Patients who underwent cinefluoroscopy at enrollment as part of the “Riata Lead Evaluation Study” will not be required undergo another baseline cinefluoroscopy. In patients with evidence of externalized conductors, the following chest x-rays will be collected, if available: a) earliest chest x-ray or imaging study showing an evidence of externalized conductors or other visual lead anomalies and b) latest chest x-ray or imaging study that does not show any evidence of externalized conductors or other visual lead anomalies.

Data will be collected on the patient demographics (gender, age, medical history, history of electrical dysfunctions in the past, etc). Lead electrical performance will also be evaluated.

For the purposes of this study, a patient is considered enrolled upon signing of the consent form and collection of data at enrollment visit. Data previously collected from patients enrolled in other ongoing SJM registries may be used for this study.

Data to be captured at enrollment includes:

- RV lead capture threshold, lead pacing impedance and signal amplitude (only required if RV lead model and implant date is listed in Table 1)*
- LV lead capture threshold, lead pacing impedance in a bipolar configuration (only required if LV lead model and implant date is listed in Table 1)
- High Voltage Lead impedance (HVLI) testing – mandatory for Current/ Promote or later ICD and CRT-D, optional for devices before Current/Promote ICD and CRT-D, and not applicable to CRT-P
- It is recommended that the Stored EGM Configuration be programmed to the following in patients with

Current/Promote or newer devices ICDs and CRT-Ds:

- RV Bipolar
- RV Unipolar Tip
- Custom: RV Coil to Can (optional)

*** Note:** If patient is pacer dependent or R-wave is not available then RV signal amplitude is not required.

Upon completion of the enrollment visit, complete the enrollment case report form (CRF) using the EDC system and submit the supportive data listed below to St. Jude Medical. Contact and address information are available on the last page of the CRF worksheet.

Enrollment CRF

Electronic device session records

Cinefluoroscopy (AP, LAO 45° or best possible LAO view, RAO 45° or best possible RAO view)

Earliest Chest X-ray or imaging study with evidence of externalized conductors or other visual lead anomalies, if available

Latest Chest X-ray or imaging study with no evidence of externalized conductors or other visual lead anomalies, if available

All eligible patients will be required to undergo the protocol specified follow-up visits. Patient participation in the study will be terminated once the 36 month visit is completed or after all leads being followed by the study are extracted and/or abandoned and the patient is monitored for 30 days.

